1. PROJECT TITLE

InstaCare: A Prospective Study of Clinical Outcomes Following Rapid ART Initiation Among Persons with HIV and Out of Care

4. ESTIMATED DURATION OF THE STUDY

3 years

5. LAY LANGUAGE SUMMARY OR SYNOPSIS (no more than one paragraph)

The human immunodeficiency virus (HIV) continues to cause significant illness and death in the USA despite availability of effective treatment. People who are aware of their HIV status, but who are out of care and not on medications, are therefore at risk of developing HIV related health problems. In addition, people with HIV who are out of care are at greater risk of transmitting HIV compared to people on HIV treatment with suppressed levels of virus in plasma. To date, there are no interventions that have been shown to successfully link this “out of care” population back into care and successfully maintain viral suppression.

This study will test a strategy of providing immediate HIV therapy drugs, linkage to care, and a randomized intervention (60-minutes for health or diet and nutrition session). The goal of the study is to demonstrate that the 60-Minutes-for-Health intervention improves the rate of viral suppression at 24 weeks.

The use of rapid antiretroviral therapy (rapid ART), defined as the initiation of ART within 7 days of HIV diagnosis, has been associated with improved rates of linkage to care, retention in care and virological suppression after 1 year among persons newly diagnoses with HIV. In addition, the behavioral intervention, “60-Minutes-for-Health”, was shown in a pilot study to improve retention in care among PWH-OOC. We aim to undertake a study to evaluate the feasibility of providing rapid-ART to people who are aware of their HIV status, but have been out of care at the time they re-engage in care. In addition, study participants will be randomized to either the “60-Minutes-for-Health” intervention or a 60 minute diet and nutrition control session.

6. SPECIFIC AIMS

AIM 1. To compare the proportion of persons with HIV and out of care (PWH-OOC) undergoing rapid-ART initiation that are on ART with VL \leq 50 copies/mL at week 24 between those randomized to 60-Minutes-for Health vs. a time-and-attention control session at baseline.

AIM 2. To compare the proportion of participants in care at week 24 between those randomized to 60-Minutes-for Health vs. a time-and-attention control session at baseline.

AIM 3. To compare the role of genotypic susceptibility scores (GSS) derived from HIV Genosure archive resistance testing as a predictor of achieving virologic suppression on rapid ART among PWH-OOC.

AIM 4. To determine the acceptability of rapid ART among PWH-OOC using quantitative surveys and focus groups on patient-reported outcomes and perspectives at week 4.

7. BACKGROUND AND SIGNIFICANCE

HIV continues to cause substantial morbidity and mortality in the USA with over 38,000 new diagnoses in 2017¹. Historically, the majority of HIV transmissions in the USA were thought to arise from persons who were HIV infected but unaware, or who had acute HIV infection^{2,3}. However, more recent data suggests the dynamics of HIV transmission in parts of the US are changing. Fewer than 60% of PWH are retained in care and achieve viral suppression⁴. As a consequence, over 40% of HIV transmissions in the US are now estimated to arise from PWH and aware of their diagnosis but out-of-care (PWH-OOC)⁵. Local data from San Diego County support a similar shift in regional transmission dynamics⁶. Using National HIV Behavioral Surveillance data applied to local prevalence, San Diego County estimates that 90% of PWH are aware of their diagnosis and that the number of new diagnoses have declined by 21% (data through 2017)⁶. However, despite these encouraging data, the HIV Care Continuum in San Diego also demonstrates that among those diagnosed with HIV infection, only 75% have been linked to care, and of these only 60% have achieved viral suppression⁷. Together, these data suggest that strategies to engage and treat PWH-OOC may play a vital role in preventing transmission of HIV⁵.

Delays between re-linkage to care and initiation of ART may represent a missed opportunity for immediate engagement resulting in some loss to follow up. Rapid ART initiation, generally defined as ART initiation <7 days from diagnosis⁸, has been shown to improve linkage, retention and viral suppression rates compared to standard of care ART in persons newly diagnosed with HIV in low and middle income countries⁹⁻¹². In the U.S., rapid ART initiation has been associated with shorter time to virologic suppression than historically treated persons¹³. To date, no studies have investigated rapid ART among PWH-OOC¹⁴, many of whom have been previously engaged in the healthcare system, but were unable to sustain engagement¹⁵. Our group has successfully implemented rapid ART among persons newly diagnosed with HIV¹⁶. We propose to leverage this expertise to evaluate rapid ART among PWH-OOC.

Multiple brief, single-session, POC interventions have successfully changed complex HIV-related behaviors in other areas¹⁷⁻²⁷. Most of these interventions range from 15-60 minutes long and are delivered in clinic settings by a variety of people (e.g. lay health educators, outreach workers, nurses). Significant changes in behavioral outcomes include reductions in condomless sex^{17,18}, decreased incidence of sexually transmitted infections^{19,20,24}, increased odds of HIV testing²¹, returning for HIV test results²², and improvements in ART adherence²³. Most follow-up periods were 6 months or less, though one study observed significant changes over 12 months¹⁹. All but one²³ intervention integrated evidence-based motivational interviewing (MI)²⁸ and/or social cognitive theories (e.g. Information Motivation Behavioral Skills model²⁹) to inform the interventions' delivery and content. MI promotes behavior change by eliciting the individual's own motivation for change and solutions to overcome their perceived barriers to change²⁸. Social cognitive theory targets the conversation around behavioral determinants most proximal to change (i.e. correct misinformation driving decisions to avoid HIV care, build motivation by improving ART attitudes, or increase behavioral skills to navigate structural barriers like transportation²⁹).

Preliminary Data

Rapid ART. The UCSD NIH-funded Primary Infection Resource Consortium (PIRC) is the largest, most intensively studied and well-characterized cohort of people identified with acute and early HIV infection in the U.S.. Since December 2014, the PIRC has implemented a rapid ART program^{16,30} in an effort to improve uptake of ART and time to virologic suppression^{10,12,13}. Since this program began, 66 of the 69 (95.7%) participants diagnosed with acute and early HIV infection have initiated rapid ART with an integrase-based treatment regimen, with a median time from HIV diagnosis to ART start of 1 day (IQR 0-6 days). The proportion with VL suppression at 12 and 24 weeks was 80% and 98%, respectively.

“60-Minutes-for Health”: To date, there are no interventions with a strong evidence base to effectively re-engage PWH-OOC³¹. “60-Minutes-for Health” is a brief, low resource, single session, theory-based behavioral

intervention for PWH-OOC^{29,32}. In a pilot randomized controlled trial (by Co-I [name]), “60-Minutes-for Health”, was found to be acceptable and feasible and was associated with improved retention in HIV care at both 12- and 24-month follow-up among participants randomized to the intervention (87.5% and 62.5% respectively) compared to a time-and-attention control (62.5% and 25.0% respectively)³².

8. PROGRESS REPORT

N/A

9. RESEARCH DESIGN AND METHODS

The overall strategy is to perform a feasibility study of rapid ART initiation among PWH-OOC who are randomized (1:1) to an unblinded behavioral intervention “60-Minutes-for Health”, compared to a 60 minute time-and-attention control session focused on diet and nutrition.

Individuals eligible for participation will be enrolled and followed for 48 weeks. They will be offered a same day (or within 1 week) appointment to enable the initiation of ART within 7 days of contact. Eligible individuals, after completing informed consent, will start ART for HIV with Bictegravir/Emtricitabine/tenofovir alafenamide (B/F/TAF) or appropriate alternative therapy if B/F/TAF is not thought to be an optimal regimen. Individuals will undergo computer-generated randomization (1:1) to onsite 60-Minutes-for Health intervention vs an onsite theory-based time-and-attention control session focused on diet and nutrition. After completion of the intervention participants will receive standard-of-care case management services between day 0 and week 4. A 60-day supply of B/F/TAF or alternative will be provided for participants of both study arms. The timeline of visits and study interventions is summarized in **Table 1**.

Table 1. Schedule of Evaluations

Study Assessment	Baseline (Day 0)	Wk 1	Wk 2	Wk 4	Wk 4-8	Wk 12	Wk 24	Wk 36	Wk 48
Assessments									
Eligibility checklist	X								
Informed Consent/HIPAA	X								
Randomization	X								
Release of information ⁴	X			X			X		X
Limited history ⁵	X								
Concomitant medications	X								
Baseline Risk Assessments	X								
Follow-up Risk Assessments				X			X		X
Linkage to Care Assessment	X			X		X ⁶	X	X ⁶	X
STI Treatment/Referral Tracking ⁷	X								
Targeted physical examination	X								
Historical ART assessment	X								
ART Adherence Monitoring		X	X	X			X		X
Adverse Event Monitoring	X	X	X	X			X		X
Ensure Provision of ART	X ⁸	X	X	X ⁸					
ART acceptability survey				X					
Behavioral Services									
60 Min Intervention vs. Control	X								
Case Management	X	X ⁶	X ⁶	X					
Telephone follow-up		X	X						

Focus Group (optional)					X				
Laboratories									
INSTI HIV Rapid Test ⁹	X								
HIV Ultra RNA PCR	X						X		X
CD4/CD8 Panel	X								
GC/CT NAT (x3 sites)	X								
Syphilis EIA	X								
w/reflex to titer and TP-PA	X								
Comprehensive Metabolic Panel	X								
CBC w/diff	X								
HepBsAg	X								
HIV Genosure archive resistance test (w/Integrase)	X ³								
Urine Pregnancy test ¹	X								
Specimen Collection									
Plasma Bank	X								
PBMC for cell pellet	X								
Stipends									
Study stipend ²	X			X	X		X		X

¹ In women any time pregnancy is suspected

² Compensation rates: Day 0 [\$20]; Survey Wk 4 [\$20]; Focus Group [\$50]; Wk 24 [\$50]; Wk 48 [\$75].

³ Sample is banked for future analysis

⁴ Baseline and at any time a new care provider is identified

⁵ Medical history, STI, HIV and Hepatitis

⁶ Phone call, email, text message, WhatsApp message, Facebook Messenger, and other participant-approved methods will be used to contact participant

⁷ Complete for participants who test positive for Syphilis, Gonorrhea and/or Chlamydia at their Day 0 visit

⁸ Study-provided ART will be dispensed at week 0 and 4

⁹ For participants without documentation of HIV positive test results

Antiretroviral Therapy (ART) drugs: Drugs proposed for use in the study are currently standard of care for PWH and are all FDA approved. For participants without a clinical history or documented evidence of integrase inhibitor resistance, a regimen of bictegravir, emtricitabine & tenofovir alafenamide (B/F/TAF) will be offered. For individuals with evidence of integrase inhibitor resistance, an alternative ART regimen will be determined, based on prior treatment regimens – in collaboration with the participants primary care physician.

Clinical assessments: All subjects will undergo history and physical examination at baseline (Day 0) for the purposes of documenting features consistent with HIV infection, subject demographics, income, insurance status and employment status. Adverse event monitoring and reporting will start at baseline and continue at each study visit. Serious adverse events, grade 2 rashes, and all grade 3 or 4 adverse events will be reported in line with the International Conference on Harmonization (ICH) guidelines.

Laboratory Assessments

HIV Monitoring Laboratories – All subjects will have an HIV rapid test performed on Day 0 on confirm HIV status if documentation of HIV status is not available to determine study eligibility. HIV related laboratories including: viral load (6 ml) and CD4 cell counts (3 ml). A 6 ml blood sample will be banked for future HIV drug resistance testing to assess ART resistance mutations (HIV GenoSure Archive). HIV viral load testing will be repeated at weeks 24 and 48.

Hepatitis Laboratories: Blood (6 ml) will be collected to test for hepatitis B virus surface Ag. If subjects are identified as HBV, they will be referred for case management to provide linkage to care and treatment.

STI screening will occur at Baseline (Day 0) as defined in Table 1. Urine, throat and rectal swab specimens will be sent for GC/CT NAT and blood will be sent for RPR (syphilis). Testing for syphilis will involve collection of 6 ml of blood. All patients will be informed of their STI test results. If any STIs are identified, notification will occur by phone or in person, and referral will be made to subject's primary medical doctor or to a public health clinic for treatment. Negative STI results will be provided via participants preferred method of communication (text, e-mail, or phone). STI reporting will be completed according to state requirements.

Safety Laboratories: A urine pregnancy test will be performed at any time during study participation that pregnancy is suspected.

Biological Specimens

Plasma and peripheral blood mononuclear cells (PBMC) – whole blood will be collected for blood plasma and PBMC (20 mL) for cryopreservation.

The total blood drawn for the screening and first four (4) study visits (12 weeks) is approximately 50 ml.

Additional study assessments: Linkage and retention in care – the number of HIV care visits ≥ 90 days apart between enrolment and 24 weeks (visit window 24 weeks + 12 weeks); the number of HIV care visits ≥ 90 days apart between enrolment and 48 weeks (visit window 48 weeks + 12 weeks). The time between enrolment and first HIV primary care visit.

Baseline, follow-up and focus group assessments: Participants will take structured surveys. Answers will be recorded into Redcap. We will use validated survey instruments of known determinants predicting engagement in HIV care: (a) unmet need addressing current and past 6-month structural barriers (i.e., housing and food stability, transportation), (b) substance use assessed by the Drug Abuse Screening Test (DAST) and AUDIT-C, (c) mental health symptoms related to depression (CESD-10) and anxiety (GAD-7), (d) antiretroviral (ART) medication regimen and overall ART adherence, (e) HIV care beliefs scale, (f) internalized HIV stigma, (g) resilience, (f) HIV affect skills, (g) sexual risk behavior and (h) the Engagement in HIV care index. Participants in the focus group will be reminded to not state anything in the focus group visit that they would not want to be heard outside of the group.

Experimental study aspects: Experimental aspects of the study are listed here:

- Rapid initiation of ART among PWH-OOC: Rapid ART among PWH with newly diagnosed infection is widely used though the use among PWH-OOC, while used in some physicians' clinical practice, is not currently established standard of care and would be considered experimental
- 60-Minutes-for Health: this is a psychological intervention which seeks to correct factors underlying decisions to delay or avoid HIV care and strengthen abilities to overcome HIV care utilization barriers. This is achieved through assistance identifying and reducing misinformation guiding HIV care attendance decisions; enhancing motivation to maintain HIV care via personal health goals; building skills for coping with negative feelings related to living with HIV; and increasing self-efficacy for navigating structural barriers and maintaining HIV care amidst competing priorities. The session will be provided by staff HIV testers (trained by [name], Co-I)

Pregnancy: Participants that are pregnant at time of enrolment to the study will be eligible to participate. US HIV guidelines indicate all individuals without contraindication should start ART immediately and so rapid-ART for pregnant participants falls within established guidelines. B/F/TAF is not standard of care for pregnant individuals and so ART regimens will be selected after discussion between investigators and according to national guidelines.

Pregnant individuals will be assisted in establishing care with HIV providers with experience in treating HIV in pregnancy and will assist with establishment in care with obstetrics providers with HIV expertise if not done prior to enrolment. The schedule of evaluations will remain the same for pregnant participants.

Data collection: data collection will be performed at each visit according to the schedule of evaluations and entered into the Research Electronic Data Capture (REDCap) data management system. Participants will be requested to provide release of information (ROI) to allow capture of HIV primary care visit data, primary care visit details (clinical notes) and HIV viral load for the duration of the study (48 weeks).

Primary outcomes are:

- the proportion of individuals with HIV VL ≤ 50 copies/ml at week 24; and
- the number of clinical care visits ≥ 90 days apart between study enrollment and week 24 (window +12 weeks).

Secondary outcomes are:

- the self-reported initiation of ART;
- the proportion of participants with HIV VL ≤ 50 at week 48;
- the proportion of participants with ≥ 2 clinical care visits > 90 days apart between enrollment and week 48;
- to compare discrete genotypic susceptibility score (derived from banked archive genotype at enrolment) between individuals with and without virologic suppression at week 24 and 48; and
- to assess the acceptability of rapid ART through quantitative surveys at week 4 and among four focus groups help between week 4-8.

Statistical considerations: Based on preliminary data from the 60-Minutes-for-Health pilot study, we expect a difference of 30% in the proportion of participants with suppressed viral load at week 24 between study groups. Assuming a loss to follow-up of 20% and a 70% rate of viral suppression in the intervention arm, we will need to enroll 124 individuals to detect a significant difference ($p < 0.05$) in suppression ($\geq 30\%$) between the two groups. The proportion of participants with the primary and secondary outcomes will be compared using Fisher's exact test between intervention groups. 95% confidence intervals for the overall proportion of PWH-OOC that are on ART with HIV VL ≤ 50 copies/ml and the overall proportion that are in care at week 24 will be compared to the analogous proportions among acute and early HIV (AEH) participants undergoing rapid ART initiation. Comparison with this historical cohort will be performed using Fisher's exact test.

Collaboration with other Academic Research Groups studying Rapid ART: Coded data, that have been stripped of identifiers, from HIV infected participants may be shared with research investigators in the U.S. and abroad, to better understand the acceptability and durability of Rapid ART and to gain a better understanding of this treatment strategy in all populations. InstaCare investigators will maintain the codebook in order to access identifiers to link data sets outside of the InstaCare research study.

Collaborations with other rapid ART investigators and collaborators are anticipated that will utilize InstaCare data and will involve the statistical, modeling, and inference needs of specific projects. The needs of these studies are expected to range from traditional biostatistical design and analyses needs (e.g., formulation of testable hypotheses, power calculations, and multivariate regressions), to novel analytical techniques (next generation sequence analysis, phylogenetics, and molecular epidemiology), which are increasingly crucial for interdisciplinary biomedical research. Summary data only will be shared with Gilead - consistent with materials prepared for publication. No individual-level data will be shared.

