Recruitment to the study will occur through two routes: the first is through identification of UCSD Owen Clinic subjects eligible for recruitment and the second is through referral of participants from the emergency department, SDPHD or through social media campaign to the AVRC. Recruitment to the study will be performed by a named

member of the study team.

UCSD Owen Clinic:

- Participants will be prospectively identified by Owen Clinic and an appointment made at Owen Clinic for re-establishment of care
- At this visit, a study team member will attend UCSD Owen Clinic, assess the subject for eligibility and if eligible perform consent for the study, HIPAA consent and ROI.

AVRC:

- Participants identified through the UCSD emergency department, SDPHD or media campaign will be contacted by the study coordinator and offered an appointment at the AVRC within 7 days. Free Lyft transport will be provided by the study coordinator
- At the AVRC, the project manager will assess the subject for eligibility and if eligible perform consent for the study, HIPAA consent and ROI.

After completion of consent, HIPAA and ROI, the study coordinator will request relevant data from the subject's primary care provider. For subjects under the care of a UCSD provider, one of the study investigators will access the subject's clinical record to abstract relevant information (comorbidities, ART treatment history, HIV resistance assays (genotypes, phenotypes), substance use history, social documentation, baseline laboratory values including HIV VL)

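### No stratification by enrolment route is described and the planned Fisher test ignores route, which costs some precision and leaves chance imbalance between Owen Clinic and AVRC uncorrected

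*Combined protocol and SAP*

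**What the plan says.** Section 9 (Research Design and Methods) states: "Individuals will undergo computer-generated randomization (1:1) to onsite 60-Minutes-for Health intervention", against a diet-and-nutrition control session. Table 1 adds only that randomisation takes place at Day 0. No stratification factor, block scheme or minimisation is described anywhere.

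Section 11 states: "Recruitment to the study will occur through two routes".

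- **Owen Clinic:** the person is identified by the clinic and has "an appointment made at Owen Clinic for re-establishment of care". At that visit "a study team member will attend UCSD Owen Clinic, assess the subject for eligibility" and, if the person is eligible, takes consent.
- **AVRC:** people found through the emergency department, the county health department or the media campaign are offered a visit at the research centre within 7 days. "At the AVRC, the project manager will assess the subject for eligibility".

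The two primary outcomes (Section 9) are viral load of 50 copies/mL or less at week 24, and the number of clinical care visits at least 90 days apart from enrolment to week 24. Under Statistical considerations, the arms are compared with Fisher's exact test, with no term for route.

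**The concern.** Route is recorded before allocation, and the plan's own description gives a reason to expect it to predict outcome. The Owen participant is already at an HIV clinic, at an appointment made to resume care. The AVRC participant is at a research facility (Section 26), and linkage to an HIV clinic has still to follow. That bears directly on the care-visit outcome and less directly on suppression. The documents do not say whether the Owen enrolment visit itself counts as a care visit; if it does, the link with route is closer still.

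Neither the design nor the analysis uses this information. If one arm happens to receive more Owen participants, the planned analysis has no means of allowing for it. At stake are a modest amount of precision and the ease of defending the comparison if the baseline table shows uneven routes.

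**Working it through.** **1. The plan's sample size.** Inputs from Statistical considerations: 70% suppression with the intervention, a 30-point difference (so 40% in control), 20% loss, p < 0.05. Power and sidedness are not stated; I assume 80% and two-sided.

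- Uncorrected: n = [1.96√(2 × 0.55 × 0.45) + 0.842√(0.7 × 0.3 + 0.4 × 0.6)]² / 0.3² = 41.97 per arm.
- Continuity-corrected: (41.97/4) × [1 + √(1 + 4/(41.97 × 0.3))]² = 48.4, rounded up to 49.
- With 20% loss: 49/0.8 = 61.25, rounded up to 62 per arm, **124 in total**. The plan's figure is reproduced. Exact Fisher power at 49 per arm is 81.5%.

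**2. Size of a chance imbalance in route.** The documents give no route shares, so the Owen share q is assumed. With n per arm and N = 2n, the SD of the between-arm difference in Owen share is √[q(1−q) × (2/n) × N/(N−1)].

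| Participants | q | SD (points) | 95% range (points) |
|---|---|---|---|
| 124 enrolled | 30% | 8.3 | ±16.2 |
| 124 enrolled | 50% | 9.0 | ±17.7 |
| 98 evaluable | 10% | 6.1 | ±11.9 |
| 98 evaluable | 25% | 8.8 | ±17.2 |
| 98 evaluable | 50% | 10.2 | ±19.9 |

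The chance of a difference of 10 points or more with 62 per arm (hypergeometric) is 24% if exactly 37 of 124 come from Owen and 21% if exactly 62 do. If the Owen count is left random, the figures are 20% and 24%.

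**3. Effect on the estimate.** Shift in the risk difference = imbalance × outcome gap between routes. The gap is also assumed. At 98 evaluable and q = 50%, the standard error of the risk difference is √[(0.7 × 0.3 + 0.4 × 0.6)/49] = 9.6 points.

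| Route gap | 95% range of shift | Share of variance, (10.15 × gap / 9.58)² |
|---|---|---|
| 10 points | ±2.0 points | 1% |
| 20 points | ±4.0 points | 4% |
| 30 points | ±6.0 points | 10% |

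**4. What the alternatives gain.** Simulation with 49 per arm, equal routes, average rates of 70% and 40%, route gaps of 10, 20 and 30 points, and 20,000 runs per setting. Type I error was simulated at 50% in both arms.

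- Fisher, unstratified allocation: power about 81–82%, type I error about 3.2–3.5%.
- Fisher, allocation stratified by route: power about 81–83%, type I error about 2.6–3.4%.
- Unadjusted chi-square, unstratified allocation: power about 87%.
- Cochran-Mantel-Haenszel by route without continuity correction, stratified allocation: power about 87%, 88% and 89% for the three gaps, type I error about 5%.

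Most of the step from Fisher to Cochran-Mantel-Haenszel therefore comes from leaving a conservative test. Route adjustment itself adds about 0–3 points of power. Stratifying the list while keeping Fisher adds about 1–2 points at most.

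**The case against.** The strongest reply is that unstratified 1:1 randomisation is valid. Chance imbalance in any covariate is already covered by the standard error and the test's error rate. That is correct: a reader might infer that route imbalance biases the result or produces false positives, and step 4 shows that it does not.

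A reader might also infer that the routes differ throughout. The documents support only part of this.

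- **Transport:** for AVRC referrals "Free Lyft transport will be provided by the study coordinator", but Sections 19 and 20 offer travel help to any participant who needs it.
- **Records:** "For subjects under the care of a UCSD provider, one of the study investigators will access the subject's clinical record" ties direct access to having a UCSD provider, not to route. One AVRC source is the UCSD emergency department, and release of information is requested from everyone.
- **Outcome capture:** the week 24 viral load is a scheduled study test for all, so any difference in capture would concern care visits.
- **Staff:** Section 11 separates the routes only on who assesses eligibility and takes consent. The session is given by trained HIV testers, with no split by route (Section 9).

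The route shares and gaps are also assumptions, and a 30-point route gap is as large as the whole planned treatment effect. Finally, the documents may omit a scheme that exists, so the accurate statement is that none is described. All of this stands. It leaves a small point about precision, resting mainly on the Owen enrolment visit being a care visit by design.

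**Conclusion.** The point holds as a low-priority improvement. No stratification is described, the planned test ignores route, and route is known before allocation and plausibly prognostic, chiefly for care visits. The consequence is somewhat lower precision and comparability, not an invalid comparison. An imbalance of 10 points or more would be unremarkable, but its likely effect on the suppression difference is at most about 2–6 points (95% range), below one standard error and well below the planned 30 points.

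These sizes assume an Owen share of 30–50% for the imbalance, an even split for the shift, and route gaps of 10–30 points; smaller shares or gaps give smaller shifts. For care visits the same imbalance figures apply, but the documents give no planning rates from which to size the effect.

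**What to change.** In Section 9, describe the allocation method and stratify the list by enrolment route (Owen Clinic or AVRC), using permuted blocks of randomly varying size.

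Under Statistical considerations, replace the unadjusted Fisher comparison of week 24 suppression with a Cochran-Mantel-Haenszel test stratified by route, with a Mantel-Haenszel risk difference and 95% confidence interval. Include route in the analysis of the care-visit outcome, and say whether that outcome is analysed as a count or a proportion and whether the enrolment visit counts. Report route by arm in the baseline table.

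If enrolment has begun, leave the randomisation alone and pre-specify the route-adjusted analysis before outcomes are compared by arm. That keeps most of the benefit.

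The cost is a second allocation list and a few sentences. N = 124 is unchanged, and no visits or staff are added. The one downside is that blocks within route are slightly more predictable in an unblinded trial, which varying block sizes limit.

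### Table 1 marks a Day 0 pregnancy test, but its footnote and the text tie the test to suspicion, so the plan does not clearly require pregnancy status before ART is chosen

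*Combined protocol and SAP*

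**What the plan says.** All of the relevant text is in Section 9 (Research Design and Methods).

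- **Table 1** marks the urine pregnancy test in the Day 0 column and in no other. Footnote 1, attached to the row label, reads "In women any time pregnancy is suspected".
- **Safety Laboratories** repeats the condition: "A urine pregnancy test will be performed at any time during study participation that pregnancy is suspected".
- **Antiretroviral Therapy (ART) drugs** sets the default: "For participants without a clinical history or documented evidence of integrase inhibitor resistance, a regimen of bictegravir, emtricitabine & tenofovir alafenamide (B/F/TAF) will be offered". Pregnancy is not mentioned there.
- **Pregnancy** makes pregnant participants eligible, supports starting ART immediately, and states: "B/F/TAF is not standard of care for pregnant individuals and so ART regimens will be selected after discussion between investigators and according to national guidelines". It also promises help in finding HIV and obstetric providers with the right experience.
- **The opening design paragraphs** allow an alternative where B/F/TAF is not judged optimal, and aim to start ART within 7 days of contact.

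**The concern.** The plan has a separate route for choosing ART in pregnancy. That route works only if the pregnancy is known when the regimen is chosen, and no sentence clearly requires this. Pregnant people are eligible, so eligibility screening does not force the question either. If a site follows the footnote and the text, a participant whose pregnancy raises no suspicion at Day 0 is not tested and is offered B/F/TAF under the general rule. The regimen discussion would be missed, and so would the help with obstetric and specialist HIV care. Two sites, or two staff members, could reasonably read the schedule differently.

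**Working it through.** The plan gives no figure to reproduce. The check sets the relevant texts side by side, followed by a bound on the cost of the remedy.

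**Step 1. What does the Day 0 mark mean?** Two readings are possible.

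- *Reading A:* the mark is a scheduled test, and footnote 1 adds later tests on suspicion.
- *Reading B:* footnote 1 is the condition on the mark, so the test is done only on suspicion.

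**Step 2. How do other row-label footnotes in Table 1 behave?**

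| Footnote | Row | Wording | Relation to the marks |
|---|---|---|---|
| 7 | STI treatment and referral tracking | "Complete for participants who test positive for Syphilis, Gonorrhea and/or Chlamydia at their Day 0 visit" | Restricts the Day 0 mark |
| 9 | HIV rapid test | "For participants without documentation of HIV positive test results" | Restricts the Day 0 mark |
| 4 | Release of information | "Baseline and at any time a new care provider is identified" | Names baseline plus a trigger, but the row is also marked at weeks 4, 24 and 48 |

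Footnotes 7 and 9 favour Reading B. For footnote 9 the HIV Monitoring Laboratories text confirms the restriction: "All subjects will have an HIV rapid test performed on Day 0 on confirm HIV status if documentation of HIV status is not available". Footnote 4 shows that the authors could write baseline plus a trigger when they meant it, and footnote 1 lacks that form. But the extra marks in footnote 4's row show that footnotes in this table do not reliably define their marks. Drafting style therefore cannot settle the matter.

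**Step 3. Does the body text settle it?** Safety Laboratories mentions suspicion and nothing else, which favours Reading B. It does not say that testing is done *only* on suspicion, so Reading A survives.

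**Step 4. What follows under each reading?**

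- *Reading A:* everyone to whom the row applies is tested at Day 0. Even so, nothing says that the result must be available before ART is chosen.
- *Reading B:* an unsuspected pregnancy is not tested for, the B/F/TAF default applies, and the Pregnancy paragraph is never triggered.

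**Step 5. Burden of the remedy.** Planned enrolment is 124 (Section 10). The documents do not give the share of participants who could be pregnant, so the shares below are assumptions. Added Day 0 tests = 124 × share:

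- 10%: 124 × 0.10 = 12.4, about 12
- 20%: 124 × 0.20 = 24.8, about 25
- 30%: 124 × 0.30 = 37.2, about 37
- Ceiling, if every participant could be pregnant: 124 × 1 = 124
- Under Reading A: 0

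These figures measure the cost of the change, not the size of the problem. The number of unsuspected pregnancies cannot be derived from the documents.

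**The case against.** The strongest reply is the Day 0 mark itself. If suspicion at any time were the whole rule, a single mark at Day 0 would be odd, because suspicion can arise at any visit. A baseline test with further tests on suspicion fits the table at least as well, and then what remains is loose wording. This stands as far as it goes. A reader might infer that the plan has no baseline pregnancy test, or that suspicion is established as the sole trigger. The documents do not support that: the mark is there, and no sentence cancels it.

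A second reply is that a pregnancy would often come to light anyway. Day 0 includes a medical history, a physical examination and survey questions on sexual risk, and Section 11 provides for requesting relevant records from the primary care provider. That Section 11's list of items abstracted from UCSD records does not name pregnancy shows little, since the list includes comorbidities. The six-month criterion in Section 10 concerns HIV clinics only and does not exclude obstetric or emergency care. These routes narrow the gap. They do not close it, because none is stated to establish pregnancy status before the regimen is chosen. Discretion to use an alternative regimen helps only when the pregnancy is known. The follow-up contacts at weeks 1, 2 and 4 come after study ART has been dispensed at Day 0.

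A third reply is that no harm has been shown. That is correct. A reader might infer that participants would be exposed to a dangerous drug. The plan says only that B/F/TAF is not standard of care in pregnancy. It does not call the regimen contraindicated or harmful, and it supports immediate ART for pregnant participants.

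**Conclusion.** The point holds as a conflict between the Day 0 mark and the suspicion wording. The plan does not clearly require pregnancy status to be known before ART is chosen, and on one fair reading an unsuspected pregnancy would receive the regimen that the Pregnancy paragraph sets aside. That consequence rests on reading footnote 1 as a condition on its mark, which is plausible but not established. The lack of clarity itself does not depend on which reading was intended.

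The point is small: an optional improvement of low priority on a minor safety matter. The number affected is unknown, and the documents support no rate of harm. The randomised comparison, sample size and primary analysis are untouched, since the ART rule is the same in both arms.

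**What to change.** Reword footnote 1 and the Safety Laboratories sentence to say: *at Day 0 in all participants who could be pregnant, with the result available before the ART regimen is chosen and dispensed, and at any later time pregnancy is suspected.* In the ART drugs paragraph, make the B/F/TAF rule subject to the Pregnancy paragraph. The choice of regimen stays with the investigators, as now.

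The cost is wording in three places plus the urine tests bounded above, at a visit where urine is already collected for gonorrhoea and chlamydia testing. The one real downside is a possible short delay to the first dose after a positive result, while the discussion that the plan already requires takes place. The 7-day target for starting ART leaves some room for that. If a scheduled Day 0 test was always intended, the same wording removes the ambiguity and adds no tests.
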